#### **6.4.1.2. Between groups assessment**

Exploratory comparisons between the investigational RSV groups and the Placebo groups will be done in terms of the percentage of subjects, overall doses, reporting any Grade 2/3 AE during the 7-day follow-up period (Day 1-7) after vaccination, and/ or any fever  $>38.5^{\circ}\text{C}$  during the 7-day follow-up period (Day 1-7) after vaccination, and/ or any vaccine-related SAE during the 7-day follow-up period (Day 1-7) after vaccination.

The standardized asymptotic 95% CI for the following differences will be computed:

- RSV\_Ld minus Placebo\_Ld
- RSV\_Md minus Placebo\_Md
- RSV\_Hd minus Placebo\_Hd

**6.4.2. Additional considerations****6.4.2.1. Additional safety analysis**

For the analysis of safety, the percentage of subjects reporting each individual solicited local AE (any, each grade, resulting in medically attended visit) during the 7-day follow-up period after vaccination will be tabulated based on maximum intensity per subject for each study vaccine for each group. The percentage of subjects reporting each individual solicited general AE (any, each grade, any related, any Grade 2 related, any Grade 3 related, resulting in medically attended visit) during the 7-day follow-up period after vaccination will be based on maximum intensity per subject for each study vaccine for each group.

**6.4.2.2. Exclusion of implausible solicited Adverse Event**

Some local and systemic adverse events will be directly measured by the subject and will not be subject to a reconciliation process, even if they are biologically implausible. Therefore, these implausible measurements will be removed from the analysis but included in listings. Implausible measurements are summarized in the table below:

**Table 2 Implausible Solicited Adverse Events**

Parameter	Implausible measurements
Body temperature	$\leq 33^{\circ}\text{C}$ or $\geq 42^{\circ}\text{C}$
Swelling	For subjects < 6 years: Measurements < 0 mm

**6.4.2.3. Combined Solicited and Unsolicited Adverse Events**

A summary of subjects with all combined solicited (regardless of their duration) and unsolicited adverse events will be provided. Solicited adverse events will be coded by MedDRA as per the following codes

Solicited symptom	Lower level term name	Lower level term code	Corresponding Primary Term code
Pain	Pain	10033371	10033371
Redness	Erythema	10015150	10015150
Swelling	Swelling	10042674	10042674
Drowsiness	Drowsiness	10013649	10013649
Fever	Fever	10016558	10016558
Irritability/Fussiness	Irritability	10022998	10022998
Loss of appetite	Appetite lost	10003028	10003028

For clintrial.gov and EudraCT posting purposes, a summary of combined solicited and unsolicited non-serious adverse events will be produced by System Organ Class and preferred terms and according to occurrence of each event.

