9.1.3. Solicited adverse events

9.1.3.1. Solicited local (injection-site) adverse events

The following local (injection-site) AEs will be solicited:

Table 16 Solicited local adverse events

All age groups
Pain at injection site
Redness at injection site
Swelling at injection site

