**Template 21 Maximum Temperature reported during the 7-day (Days 1-7) post-vaccination period – dose X <Exposed Set>**

		Each group N =				Total N =			
				95% CI				95% CI	
Characteristics	Categories	n	%	LL	UL	n	%	LL	UL
Maximum temperature	No fever								
	Unknown temperature								
	[37.5-37.9]								
	[38.0-38.4]								
	[38.5-38.9]								
	[39.0-39.4]								
	[39.5-39.9]								
	[40.0-....								

N = number of subjects with documented dose  
 n/% = number/percentage of subjects in a given category  
 95%CI = Exact 95% confidence interval; LL = lower limit, UL = upper limit

**Template 22 Percentage of subjects reporting the occurrence of unsolicited symptoms classified by MedDRA Primary System Organ Class and Preferred Term within the 30-day (Days 1-30) post-vaccination period <Exposed Set>**

		Each group N =			
				95% CI	
Primary System Organ Class (CODE)	Preferred Term (CODE)	n	%	LL	UL
At least one symptom					
Gastrointestinal disorders (10017947)	Diarrhoea (10012735)				
	Teething (10043183)				
	Vomiting (10047700)				
General disorders and administration site conditions (10018065)	Pyrexia (10037660)				
Immune system disorders (10021428)	Seasonal allergy (10048908)				
Infections and infestations (10021881)	Conjunctivitis (10010741)				
	Otitis media (10033078)				
	Paronychia (10034016)				
	Tonsillitis (10044008)				
	Tonsillitis streptococcal (10044013)				
	Viral upper respiratory tract infection (10047482)				
Injury, poisoning and procedural complications (10022117)	Arthropod bite (10003399)				
	Face injury (10050392)				
	Head injury (10019196)				
Skin and subcutaneous tissue disorders (10040785)	Miliaria (10027627)				

RSV-Ld = Low dose ChAd155-RSV vaccine (5 x 10^9 vp)  
 RSV-Md = Middle dose ChAd155-RSV vaccine (1.5 x 10^10 vp)  
 RSV-Hd = High dose ChAd155-RSV vaccine (5 x 10^10 vp)  
 Placebo-Ld = Non-active control (0.5 ml)  
 Placebo-Md = Non-active control (0.15 ml)  
 Placebo-Hd = Non-active control (0.5 ml)  
 At least one symptom = at least one symptom experienced (regardless of the MedDRA Preferred Term)  
 N = number of subjects included in the considered cohort in each group  
 n/% = number/percentage of subjects reporting the symptom at least once  
 95% CI = exact 95% confidence interval; LL = Lower Limit, UL = Upper Limit

**Template 23 Number and percentage of subjects taking a concomitant medication during the 7- day (Days 1-7) post -vaccination period <Exposed Set>**

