**Template 29 Solicited and unsolicited symptoms classified by MedDRA Primary System Organ Class and Preferred Term within the 30-day (Days 1-30) post-vaccination period including number of events - SAE excluded <Exposed Set>**

		<each group> N =		
Primary System Organ Class (CODE)	Preferred Term (CODE)	n*	n	%
At least one symptom				
<each SOC>	<each PT term>			

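### The SAP's code table gives solicited fever a term code that conflicts with its own templates and drops the injection-site label from the three local symptoms, which distorts the combined preferred-term summaries

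*SAP*

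**What the plan says.** SAP section 6.4.2.3 announces a summary of solicited and unsolicited adverse events together, plus a version restricted to non-serious events for ClinicalTrials.gov and EudraCT, arranged by System Organ Class and preferred term. It then gives the coding rule: "Solicited adverse events will be coded by MedDRA as per the following codes". The table that follows has a lower-level-term code and a column headed "Corresponding Primary Term code". It reads "Fever 10016558 10016558" for fever, "Pain 10033371 10033371" for pain and "Erythema 10015150 10015150" for redness.

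The mock for the combined table is Template 29: "Solicited and unsolicited symptoms classified by MedDRA Primary System Organ Class and Preferred Term within the 30-day" window after vaccination, with serious events excluded.

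The other passages that bear on the point are these:
- SAP Template 22 (unsolicited events by preferred term) lists fever as Pyrexia with code 10037660. Template 28 has the same row.
- SAP section 6.4.1.1 has each unsolicited verbatim term matched to its preferred term, in MedDRA version 20.
- The protocol glossary treats a solicited-type symptom that starts outside the solicited window as an unsolicited event.
- Protocol Table 16 defines the solicited local events by site, for example "Pain at injection site".

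**The concern.** A table by preferred term works only if the same event carries the same preferred term however it was collected. For fever, the SAP's codes break that condition. An infant with fever on Day 3 is filed under 10016558, and one with fever on Day 12, reported as unsolicited, under 10037660. Both belong to the same 30-day table, but neither row answers how many infants had a fever.

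The local symptoms have a related problem. Pain, redness and swelling are collected only at the injection site, yet they are coded as plain Pain, Erythema and Swelling. In these summaries they share a row with any unsolicited event coded to the same term elsewhere on the body.

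What is at stake is the readability of the combined preferred-term table and of a summary made for public registries.

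**Working it through.** The plan gives no figure here to reproduce, so the check is a comparison of codes followed by a count.

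**Step 1. Lower-level code against term-level code (SAP 6.4.2.3).**

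| Solicited symptom | Lower-level code | Term-level code | Same? |
|---|---|---|---|
| Pain | 10033371 | 10033371 | yes |
| Redness (Erythema) | 10015150 | 10015150 | yes |
| Swelling | 10042674 | 10042674 | yes |
| Drowsiness | 10013649 | 10013649 | yes |
| Fever | 10016558 | 10016558 | yes |
| Irritability/Fussiness | 10022998 | 10022998 | yes |
| Loss of appetite | 10003028 | 10003028 | yes |

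The codes agree in 7 of 7 rows. That alone does not prove an error; it needs evidence of a different preferred term.

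**Step 2. Evidence inside the SAP.** Templates 22 and 28 give a preferred-term code for fever, Pyrexia 10037660, which differs from 10016558. The documents show no competing preferred-term code for the other six symptoms.

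**Step 3. Do the two fever codes meet in one table?** Solicited fever covers Days 1-7 after each dose in the SAP's day numbering. Fever starting on Days 8-30 is unsolicited and is matched to its preferred term. Template 29 covers both over Days 1-30, and the registry summary is also by preferred term. They therefore do meet.

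**Step 4. Site label.** Protocol Table 16 ties all three local symptoms to the injection site. The SAP table gives 0 of 3 a term that names the site. The SAP does use site-specific preferred terms elsewhere: Annex 2 lists injection site haematoma (10022066), among others.

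**Step 5. Size, with assumed counts.** The documents give no fever counts. Let N = 16 in a group, s infants with solicited fever and u with unsolicited fever. The two rows show s/N and u/N. The share with any fever lies between max(s, u)/N (full overlap) and (s + u)/N (no overlap).

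| s | u | Rows shown | Infants with any fever |
|---|---|---|---|
| 4 | 2 | 4/16 = 25.0% and 2/16 = 12.5% | 4/16 = 25.0% to 6/16 = 37.5% |
| 6 | 3 | 6/16 = 37.5% and 3/16 = 18.75% | 6/16 = 37.5% to 9/16 = 56.25% |
| 8 | 4 | 8/16 = 50.0% and 4/16 = 25.0% | 8/16 = 50.0% to 12/16 = 75.0% |

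The larger row equals the true share only when every infant with unsolicited fever also had solicited fever. The table does not show whether that is so.

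**The case against.** The strongest reply is that the split may never occur. The code table gives no System Organ Class, although the output needs one, so a programmer must consult the dictionary anyway. Deriving the preferred term from the listed lower-level term would then put fever in one row. The Pyrexia row sits in a mock table that SAP section 13 calls illustrative, and some rows there are plainly placeholders: Template 28, meant for bleeding events, lists teething and arthropod bites. The split also needs at least one unsolicited fever.

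This makes the split conditional but does not remove the error. Section 6.4.2.3 is an instruction in the body of the SAP, not a mock. If the dictionary overrides it, the listed fever code is wrong and unused. Nor would deriving the parent term restore the injection site, since the chosen lower-level terms do not name one.

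A reader might infer more than the documents support:
- **That no other table joins the two collection methods.** SAP section 6.4.1.1 and Template 16 also join them, and keep local apart from general.
- **That injection-site reactions are lost, or that a local dose signal would be hidden.** The events stay in the combined table and lose only their site label. Templates 17, 18 and 55 report them by group and dose. For adults, protocol section 1.1.6 says only that the high dose seemed more reactogenic, both locally and generally.
- **That this is the only result made public.** Protocol section 12.5 commits to posting primary and secondary endpoint results.
- **That all seven codes are wrong.** The documents show this for fever only.

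**Conclusion.** Wrong as written; minor. The fever code in SAP 6.4.2.3 conflicts with the preferred term the SAP uses elsewhere. Followed literally, it leaves Template 29 and the registry summary without a row for infants with any fever in 30 days. The three local symptoms lose their site label in the same summaries.

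The conclusion rests on two conditions for fever: the listed code is used as the preferred term, and at least one unsolicited fever is reported. The percentages are illustrations with assumed counts, not forecasts.

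The primary reactogenicity results do not change. Templates 17-20, 55 and 56 are built on symptom names, and the local and general tables of section 6.4.1.1 and Template 16 do not depend on these codes. A 30-day fever rate is not a listed endpoint.

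**What to change.** Correct the code column in SAP 6.4.2.3:
- Set the preferred-term code for fever to 10037660 (Pyrexia).
- Check the other six codes against MedDRA version 20 and enter the parent preferred term of each listed lower-level term.
- Map pain, redness and swelling to the injection-site preferred terms in that dictionary. The exact terms and codes must be taken from it, because the documents do not give them.
- Rename the column so that it clearly refers to the preferred term.
- Count each infant once per preferred term across solicited and unsolicited reports, as the footnote to Template 29 already defines.

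The cost is the revision of one SAP table before programming. No data collection or other analysis changes.

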## 7. ANALYSIS INTERPRETATION

All analyses are descriptive. Comparative analyses will be descriptive with the aim to characterize the difference in safety/reactogenicity between groups and should be interpreted with caution considering that there is no adjustment for multiplicity and that group sizes are small for these comparisons.

## 8. CONDUCT OF ANALYSES

### 8.1. Sequence of analyses

The statistical analyses will be performed in 3 steps:

A first analysis will be performed when all data (safety and immunogenicity) up to Day 61 (i.e. data that are as clean as possible) are available. Additional safety data available at the time of this analysis will be described. At this point, the statistician will be unblinded (i.e. individual subject treatment assignments will be available) and the study will be conducted in a single-blind manner, with patients remaining blinded up to study end (Day 731). Summary results may unblind some specific subjects but no individual listings will be provided and the investigators will not have access to the treatment allocation up to study end (Day 731), except in case of emergency unblinding (see Section 9.8 of the protocol).

An analysis will be performed when all data (safety and immunogenicity) up to Visit 10 (Day 366; i.e. data that are as clean as possible) are available. No individual listings will be provided.

The final analysis will be performed when all data up to study conclusion (Day 731) are available. An integrated clinical study report containing all data will be written and made available to the investigators at that time.

If the data for tertiary endpoints (additional exploratory analyses) become available at a later stage, (an) additional analysis/ analyses will be performed. These data will be documented in amendments to the study report and will be made available to the investigators at that time.

Description	Analysis ID	Disclosure Purpose (CTRS=public posting, SR=study report, internal)	Dry run review needed (Y/N)	Study Headline Summary (SHS) requiring expedited communication to upper management (Yes/No)	Reference for TFL
Final Analysis	E1_01	SR	N	Yes	
Analysis of epoch 1	E1_0X	CTRS	Y	Yes	
Up to D366	E1_0X+1		N	No	All tables from TFL dated xxxxxx

**Table 3 Endpoints assessed at different analysis time points**

Analysis	Analysis ID	Safety	Immuno	RSV/RTI
Epoch 1 (Day 60)		Solicited AE, Unsolicited AE, haematology and biochemistry, AESI(bleeding), SAE from D1-Day 61	All CMI and Humoral readout from D1-D61	
Up to D366		SAE, AESI – D1-D366	All CMI and Humoral response at D366	RSV analysis for 1 st season – D1-D366
Final (Day 731)		SAE, AESI – D1-D731	None	RSV 2 nd season – D367-D731; Overall (D1-D731)

## 8.2. Statistical considerations for interim analyses

No interim analysis is planned.

## 9. CHANGES FROM PLANNED ANALYSES

Following are the changes in the planned analysis:-

- The naming of the cohort has been changed per cDISC standards.
- Per cDISC standard, the day of first vaccination is now changed from Day 0 to Day 1.
- The study design diagram has been adapted as per cDISC format
- In secondary endpoints, specific safety endpoints for Day 1 up to D366 has been added as follows: -
  - Occurrence of SAEs from study start (Day 1) up to Day 366.
  - Occurrence of RSV-LRTI (AE of specific interest) as from Dose 1 administration up to Day 366.
  - Occurrence of RSV-RTI, RSV-LRTI, severe RSV-LRTI (according to standardized case definitions) as from Dose 1 administration up to Day 366.
- For the immunogenicity analysis, the analysis will be performed on both PPS and ES without any condition on percentage of subjects excluded
- For inclusion of subjects in PPS for analysis of immunogenicity, subjects should have received both the doses and not atleast one dose.

## 10. LIST OF FINAL REPORT TABLES, LISTINGS AND FIGURES

The TFL TOC provides the list of tables/listings and figures needed for the study report. It also identifies the tables eligible for each analyses and their role (synopsis, in-text, post-text, SHS, CTRS,...). Note that all TFL aimed to be included as post-text are noted as post-text even if these are tabulation of individual data such as listing of SAE. The post-text material contains all source material for the study report and accordingly a post-text table may be redundant with an in-text table.

The mock tables referred under column named 'layout' can be found in legacy-GSK SDD dedicated folder for standard tables and in Section 12 (Annex 2) for study specific mock table/figure/listing. The latter table/figure/listing are identified by the prefix SS\_ in the TFL Toc.

The following group names and pooled group names will be used in the TFLs, to be in line with the T-domains:

Group order in tables	Group label in tables	Group definition for footnote	Pooled Groups label in tables	Pooled definition for footnote
1	RSV-Ld	Low dose ChAd155-RSV vaccine (5 x 10  vp)	RSV	ChAd155-RSV vaccine (low/ middle/high dose pooled groups)
2	RSV-Md	Middle dose ChAd155-RSV vaccine (1.5 x 10  vp)	RSV	ChAd155-RSV vaccine (low/ middle/high dose pooled groups)
3	RSV-Hd	High dose ChAd155-RSV vaccine (5 x 10  vp)	RSV	ChAd155-RSV vaccine (low/ middle/high dose pooled groups)
4	Placebo-Ld	Non-active control (0.5 ml)	Placebo	Non active control (0.15/0.5 ml pooled groups)
5	Placebo-Md	Non-active control (0.15 ml)	Placebo	Non active control (0.15/0.5 ml pooled groups)
6	Placebo-Hd	Non-active control (0.5 ml)	Placebo	Non active control (0.15/0.5 ml pooled groups)
7 ^	Pooled	Pooled RSV + Placebo	Pooled	Pooled RSV + Placebo

^The pooled group is not in the treatment dataset but will be created for generating some tables during D366 analysis.

## 11. ANNEX 1 STANDARD DATA DERIVATION RULE AND STATISTICAL METHODS

### 11.1. cDISC specification

The analysis planned at D61, D366 and D731 is planned in cDISC format. In cDISC format, the day of vaccination is mentioned as Day 1 rather than Day 0 per protocol. Accordingly, all the timepoint will be mentioned as Day X +1. The analysis will be performed adjusting for it so that correct interval will be selected.

### 11.2. Statistical Method References

The exact two-sided 95% CIs for a proportion within a group will be the Clopper-Pearson exact CI [Clopper CJ, Pearson ES. The use of confidence or fiducial limits illustrated in the case of binomial. *Biometrika*. 1934; 26:404-413].

The standardised asymptotic two-sided 95% CI for the group difference in proportions is based on the method described in the following paper: Robert G. Newcombe, interval estimation for the difference between independent proportions: comparison of eleven methods, *Statist Med*. 1998; 17, 873-890]. The standardised asymptotic method used is the method six.

### 11.3. Standard data derivation

#### 11.3.1. Date derivation

- SAS date derived from a character date: In case day is missing, 15 is used. In case day & month are missing, 30June is used.
- Onset day for an event (ae, medication, vaccination, ...): The onset day is the number of days between the last study vaccination & the onset/start date of the event. This is 1 for an event starting on the same day as a vaccination. See SAS date derived in case the start date of the event is incomplete.
- Duration: Duration of an event is expressed in days. It is the number of days between the start & the stop dates + 1. Therefore, duration is 1 day for an event starting & ending on the same day.
- Association of an event to the primary epoch: An adverse event belongs to the primary epoch, if the onset date is before and including Visit 9 (Day 60). Any safety data collected beyond Visit 9 (Day 60) will be collected in Epoch 002.

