### **4. ENDPOINTS**

#### **4.1. Primary endpoints**

- Occurrence of AEs from first vaccination (Day 1) up to Day 61.
  - Occurrence of each solicited local and general AE, during a 7-day follow-up period after each vaccination (i.e. the day of vaccination and 6 subsequent days).
  - Occurrence of any unsolicited AE, during a 30-day follow-up period after each vaccination (i.e. the day of vaccination and 29 subsequent days).

- Occurrence of any SAE from Day 1 up to Day 61.
- Occurrence of episode of spontaneous or excessive bleeding (AE of specific interest), during a 30-day follow-up period after each vaccination.
- Occurrence of any hematological (hemoglobin level, white blood cells and platelets) laboratory abnormalities at Screening, Day 1, Day 8, Day 31, Day 32, Day 38, and Day 61.
- Occurrence of any biochemical (alanine aminotransferase, aspartate aminotransferase and creatinine) laboratory abnormalities at Screening, Day 31, and Day 61

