**5.2.2. Elimination from Per-protocol analysis Set (PPS)**

**5.2.2.1. Excluded subjects**

A subject will be excluded from the PPS for analysis of immunogenicity at Day 61 and Day 366 under the following conditions

Code	Condition under which the code is used
900	Invalid informed consent or fraud data ( Subjects receiving a code 900 should not receive any other elimination codes )
1030	Study vaccine not administered at all ( Subjects receiving a code 1030 should not receive any other elimination codes )
1050	Randomization failure
1070\$	Subjects got vaccinated with the correct vaccine but containing a lower volume
1070\$	Administration not according to protocol for reason specified by the investigator, other than side, site and route
1070\$	Site or route of study vaccine administration wrong or unknown
1070\$	Wrong replacement or study vaccine administered (not compatible with the vaccine regimen associated to the treatment number)
1070\$	Administered study vaccine reported as being the correct one but is not compatible with the vaccine regimen associated to the treatment number
1080	Vaccine temperature deviation
1090	Expired vaccine administered
1500\$	Subjects who have received only one dose of vaccination
2010	Protocol violation (inclusion/exclusion criteria)
2080	Subjects did not comply with vaccination schedule (DOSE 1 to DOSE 2 = 23-36 (days))

*\$ Attribution of code to a subject requires CRDL confirmation*

*Please note that all the elimcode has to be checked for the subject under schedule 1.*

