The percentage of subjects with unsolicited AEs within 30 days (Day 1-30) after each vaccine dose (overall doses) with its exact 95% CI will be tabulated by group and by MedDRA preferred term. Similar tabulation will be done for Grade 3 unsolicited AEs, for any causally related unsolicited AEs, for Grade 3 causally related unsolicited AEs and for unsolicited AEs resulting in a medically attended visit. The verbatim reports of unsolicited AEs will be reviewed by a physician and the signs and AEs will be coded according to the MedDRA Dictionary Version 20 for Adverse Reaction Terminology. Every verbatim term will be matched with the appropriate Preferred Term.

The percentage of subject with episode of spontaneous or excessive bleeding (AE of specific interest), during a 30-day follow-up period after each vaccination will be tabulated by group according to associated PT code presented in Section 12. The percentage of subjects with RSV-LRTI (AE of specific interest) from Dose 1 up to Day 365 and from Dose 1 up to study conclusion (Day 730) will be tabulated by group according to associated PT code presented in Section 12.

The percentage of subjects with SAE within 30 days (Day 1-30) after each vaccine dose with its exact 95% CI will be tabulated by group and by MedDRA preferred term. Similar table will be generated for SAE from Dose 1 up to Day 61, from Dose 1 up to Day 366 and from Dose 1 up to Day 731.

SAEs reported throughout the study and AE of specific interest will be described in detail.

The percentage of subjects using concomitant medication (any medication, any antipyretic/ analgesic and any antipyretic taken prophylactically, respectively) during the 7-day follow-up period (Day 1-7) and during the 30-day follow-up period (Day 1-30) will be summarized by group after each vaccine dose and overall.

For each group and for each hematology and biochemistry parameter:

- The percentage of subjects having hematology and biochemistry results below/above/within the local laboratory normal ranges will be tabulated by timepoint and toxicity grading scale.
- The maximum grading from Screening up to Visit 9 (Day 61) will be tabulated by grading the safety laboratory values according to toxicity criteria Grading scale adapted from [Division of AIDS, 2003], [Division of AIDS, 2004] and [Division of AIDS, 2007].

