### 11.3.2. Dose number

- The study dose number is defined in reference to the number of study visits at which vaccination occurred. More specifically dose 1 refers to all vaccines administered at the first vaccination visit while dose 2 corresponds to all vaccinations administered at the second vaccination visit even if this is the first time a product is administered to the subject.
- Relative dose: the relative dose for an event (AE, medication, vaccination) is the most recent study dose given before an event. In case the event takes place on the day a study dose is given, the related dose will be that of the study dose, even if the event actually took place before vaccination. For instance, if an adverse event begins on the day of the study vaccination but prior to administration of the vaccine, it will be assigned to this dose. In case a study dose is not administered and an event occurs after the subsequent study dose (eg 2nd study dose), the relative dose of the event will be study dose associated to the subsequent study dose (eg dose 2).
- The number of doses for a product is the number of times the product was administered to a subject.
- The incidence per dose is the number of vaccination visits at which an event was reported among all vaccination visits.

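### SAP 11.3.1 sets a missing AE start day to the 15th without regard to the vaccination date, so a partial-date event can land before Dose 1, outside the 30-day window, or under the wrong dose

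*SAP*

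**What the plan says.** SAP 11.3.1 (Date derivation) gives one rule for any incomplete date: "In case day is missing, 15 is used. In case day & month are missing, 30June is used". The next bullet defines the onset day: "The onset day is the number of days between the last study vaccination & the onset/start date of the event", with the convention "This is 1 for an event starting on the same day as a vaccination". It then refers partial event dates back to the first rule: "See SAS date derived in case the start date of the event is incomplete".

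SAP 11.3.2 attributes events to doses: "the relative dose for an event (AE, medication, vaccination) is the most recent study dose given before an event". Its same-day exception assigns an event on a vaccination day to that day's dose. SAP 11.3.5 repeats this.

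The derived day decides where an event is counted. The primary endpoint in SAP 4.1 is "Occurrence of any unsolicited AE, during a 30-day follow-up period after each vaccination (i.e. the day of vaccination and 29 subsequent days"). SAP 6.4.1.1 tabulates "The percentage of subjects with unsolicited AEs within 30 days (Day 1-30) after each vaccine dose (overall doses"), and treats SAEs and bleeding events over 30-day periods as well.

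No section compares an imputed date with the dose date, floors it at the dose, or keeps a partial-date event in its window. SAP 11.3.3 does warn that an incomplete birth date can distort age; there is no similar warning for AEs.

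**The concern.** The protocol collects AEs that start within 30 days after a dose (section 9.3.1) and sends conditions present before the first vaccination to medical history (section 9.1.1). An AE record with a missing start day will therefore usually be a post-vaccination event. The imputation ignores this and can give a date that contradicts it.

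An event placed before Dose 1 has no preceding dose, and SAP 11.3.2 does not say what happens to it. An event placed past Day 30 leaves the primary unsolicited-AE table. SAP 11.3.5 then counts the subject as event-free unless another event was reported. With about 8 to 16 subjects per group, one misplaced event moves a group percentage by 1/16 = 6.25 to 1/8 = 12.5 points.

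**Working it through.** The plan gives no figure on this point, so there is none to reproduce. The inputs are:

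- imputed day 15, or 30 June (SAP 11.3.1);
- onset day = imputed date − last vaccination date + 1 (SAP 11.3.1);
- window Day 1 to Day 30 after each dose (SAP 4.1 and 6.4.1.1);
- Dose 1 to Dose 2 gap of 23 to 36 days (SAP 5.2.2.1), planned at 30.

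Uniform vaccination dates and uniform true onset over Days 1 to 30 are assumptions of this check.

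**Single cases**

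- Dose 1 on 20 January, true onset 25 January (Day 6), day missing. The imputed date is 15 January, 5 days before Dose 1.
- Dose 1 on 5 January, true onset 2 February (Day 29). The imputed date is 15 February, Day 42 after Dose 1. If Dose 2 was given on 4 February, the event becomes Dose 2, Day 12.
- Dose 2 on 4 February, true onset 2 March (Day 27). The imputed date is 15 March, Day 40, outside both windows.

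**Own-dose window, 30-day months.** Let the dose fall on day d.

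- For d = 16 to 30, the 31 − d onset days left in that month are imputed before the dose: 15 + 14 + … + 1 = 120.
- For d = 1 to 15, the d − 1 onset days in the next month are imputed past the window: 0 + 1 + … + 14 = 105.
- Total: (120 + 105)/(30 × 30) = 225/900 = 25%.

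**Own-dose window, 2018 calendar.** Over 365 × 30 = 10,950 combinations, 13.9% fall before the dose, 11.5% fall beyond Day 30, and 74.6% stay.

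**Both doses together.** Leaving one dose's window is not the same as leaving both:

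| Gap | True dose | Outside both windows | Moved to the other dose's window |
|---|---|---|---|
| 30 days | 1 | 13.9% | 11.5% |
| 30 days | 2 | 11.5% | 13.9% |
| 36 days | 1 | 13.9% + 7.6% = 21.5% | 4.0% |
| 36 days | 2 | 11.5% + 8.5% = 20.0% | 5.4% |

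The average outside both windows is (13.9 + 11.5)/2 = 12.7%, about 13%, at 30 days. At 36 days it is (21.5 + 20.0)/2, about 21%.

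**Day and month missing (30 June).** Relative to the event's own dose, 46.4% fall before it, 45.3% fall beyond Day 30, and 8.2% stay.

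**The opposite error.** Of events truly starting on Days 31 to 60 after a dose, 13.9% are pulled into Days 1 to 30 of that dose.

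**The case against.** The strongest reply is that the rule will rarely be used, and that much of what it moves is not lost.

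- **Few partial dates.** Parents keep diary cards, which the investigator verifies with them at Days 7, 30, 37 and 60 (protocol 6.6.16). SAEs and AEs of specific interest are reported within 24 hours (protocol 9.4). Omissions in the eCRF are queried and entries are source-verified (protocol 12.1 and 12.2). This stands: every percentage above is conditional on a partial date, and the documents give no rate.
- **Other displays catch the events.** SAEs are also tabulated from Dose 1 to Days 61, 366 and 731, and SAEs and AEs of specific interest are described in detail (SAP 6.4.1.1). SAP 13.1 lists unsolicited AEs after 30 days. Solicited AEs rest on daily recordings. This stands too, and it narrows the exposed outcome mainly to non-serious unsolicited AEs.
- **Switching dose is not loss.** The unsolicited-AE table is taken over all doses, and its mock-up (Template 22) counts subjects without a dose split. A reader might infer from the 25% that a quarter of partial-date events drop out of the primary safety window. The documents do not support that: at the planned gap about half of the 25% stays in a window under the other dose.
- **Direction.** A reader might also infer that the rule favours the vaccine. It applies equally to both arms of each 1:1 step, all analyses are descriptive (SAP 7), and some late events are pulled in. That offset is weak for non-serious AEs after Dose 2, because required collection stops at 30 days. For those events the net effect is undercounting, but in both arms.

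None of this removes the defect: the rule as written can place a collected post-vaccination event before vaccination.

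**Conclusion.** The point holds as a minor but real fault in a stated rule. Among unsolicited AEs and SAEs with only the start day missing, about a quarter leave their own dose's 30-day window. About 13% leave both windows with a 30-day gap, and about 21% with the longest allowed gap of 36 days. With the month also missing, only about 8% stay in their own window.

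These figures rest on uniform vaccination dates and onset days. The effect on the reported tables cannot be computed, because the number of partial dates is unknown; it is probably small. The case for changing the rule is that groups are small enough for one event to matter and the correction is cheap.

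**What to change.** Add a sentence to SAP 11.3.1, for AEs only, before the Day 61 analysis:

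- Keep the 15th as the default, restricted to dates compatible with the recorded month and year and any recorded stop date.
- If the result falls before Dose 1 but the known month and year allow onset on or after Dose 1, use the Dose 1 date.
- If it falls outside every 30-day window but the known month and year overlap one, use the nearest compatible date inside that window.
- Apply the same limits when the month is also missing.
- Where the partial date fits both doses, use the dose recorded by the investigator or on the diary card if available, and do not default to the later dose.

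An event that truly began inside a window has a recorded month that overlaps it, so with only the day missing none would be left outside both windows. Some dose switching remains where no dose is recorded.

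A simpler rule would use the latest compatible vaccination date whenever the month matches, and otherwise the first of the month. It overcorrects. With a 30-day gap it moves 49% of missing-day Dose 1 events to Dose 2. It also puts about 85% of all missing-day events in Days 1 to 7 of a dose, against a true 7/30 = 23%. That would feed the 7-day tables and the between-group comparison in SAP 6.4.1.2.

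The cost is one SAP sentence. A few pre-dose or post-window events may be counted as in-window, and events moved up to the Dose 1 date will appear on Day 1.
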